2 RATIONALE AND BACKGROUND

2.1 STUDY RATIONALE

Patients with midfacial pain or uncomfortable pressure are often presumed to have rhinosinusitis. Despite treatment for sinusitis, a significant number of patients continue to complain of facial pain without clear etiology, which can be frustrating for both the patient and clinician. If this facial pain is not due to a presumed diagnosis of “sinusitis” as assessed by failure to respond to medical management, a negative endoscopic evaluation and no significant radiologic evidence of sinusitis, then the patient has idiosyncratic facial pain unrelated to but mimicking sinusitis. One possible etiology for patients with an ongoing complaint as described above is migraine-related facial pain. Changing the paradigm as to how these sinus patients are both evaluated and treated could have important public health benefits.

There can be significant overlap between the symptoms of migraine disease and those of rhinosinusitis, which results in misdiagnosis and unnecessary treatments.[1-3] Several studies indicate that the majority of patients with self-perceived sinus headache satisfy the diagnostic criteria for migraine. A study of 2991 patients by Schreiber et al found that 88% of patients with self-reported or physician-diagnosed sinusitis met diagnostic criteria for migraine.[4] Similarly, Eross et al reported in a study of 100 patients that 88% with self-perceived sinus headaches met criteria for migraine and other primary headache disorders.[5] Another study of 130 patients with migraines and no evidence of sinusitis found that 81.5% were misdiagnosed with sinusitis.[6]

Consideration and institution of migraine-specific treatment in patients who have midfacial pain or pressure mimicking rhinosinusitis could have a significant public health impact. This impact would include reduction of unnecessary treatments such as repeated or prolonged antibiotics and endoscopic sinus surgery [7, 8], and improved quality of life and cost savings for the patient and stakeholders supporting health care. Calcitonin gene-related peptide receptor (CGRPR) antagonists have demonstrated clinical efficacy in migraine prevention.[9, 10] Erenumab, a monoclonal antibody binding to the CGRP receptor, was FDA approved in 2018 for the prevention of migraines. Therefore, erenumab has the potential to be an effective treatment option for this patient population.

2.2 BACKGROUND

Approximately 30 million adult Americans, or 12% of the US population, are diagnosed with rhinosinusitis (RS) annually and antibiotics are prescribed in 82% of associated office visits. This includes patients with acute rhinosinusitis (ARS), in which symptoms last <4 weeks, recurrent acute rhinosinusitis (RARS), in which a patient has 4 or more acute episodes in a year, and chronic rhinosinusitis (CRS), in which symptoms last >12 weeks [6]. However, several studies suggest that many of these patients have no objective evidence of sinusitis on endoscopy or imaging, but rather meet criteria for migraine or other

primary headache disorder.[1, 5-8] This leads to ineffective treatments and associated morbidity, such as antibiotic resistance, persistent symptoms, and unnecessary surgery.

Patients with idiosyncratic facial pain may actually have chronic upregulation of any one or more branches of the trigeminal nerve leading to the perception of facial pressure and pain with secondary autonomic symptoms such as nasal congestion, rhinorrhea, tearing, and facial swelling. In other words, they may have a complex spectrum of nervous system dysfunction that can mimic RS. Despite this, studies have demonstrated that patients undergo invasive sinus procedures at least in part due to the lack of effective treatments for idiosyncratic facial pain.[11] Medications commonly prescribed for migraine prevention, such as valproate or topiramate, are often ineffective or poorly tolerated. Moreover, patients often are not candidates for such medications because they do not have a classic presentation of migraines.

2.3 RISK/BENEFIT ASSESSMENT

2.3.1 KNOWN POTENTIAL RISKS

As of 16 May 2020, approximately 6,550 people have received erenumab in research studies. Since it was first approved for sale on 17 May 2018, approximately 423,800 people have been prescribed erenumab (Aimovig®) for treatment as of 16 May 2020. The most common adverse reactions (incidence $\geq 2\%$ and at least 2% greater than placebo for either 70 mg or 140 mg doses) in Phase 3 trials were injection site reactions (5-6%), constipation (3%), and cramps/muscle spasms (2%). 1.3% of patients in these trials withdrew from treatment because of adverse events. The most frequent injection site reactions were pain, erythema, and pruritus.

Hypersensitivity reactions, including rash, angioedema, and anaphylaxis, have been reported with erenumab in post-marketing experience. Most hypersensitivity reactions were not serious and occurred within hours of administration, although some occurred more than one week after administration.

Constipation with serious complications has also been reported in the postmarketing setting. The majority of cases occurred after the first dose of erenumab. There were cases that required hospitalization with or without surgery.

Antibodies against erenumab have been seen in clinical studies. The incidence of antibody development was 6.2% in patients receiving 70 mg once a month and 2.6% in patients receiving 140 mg once a month. No side effects associated with these antibodies were observed. The side effects of using erenumab in combination with other drugs are unknown at this time.

Constipation with serious complications has been reported following the use of Aimovig® in the postmarketing setting. There were cases that required hospitalization, including cases where surgery was necessary. In a majority of these cases, the onset of constipation was reported after the first dose of Aimovig®; however, patients have also presented with constipation later on in treatment. Patients

who take medications that decrease the movement of the stomach and intestines may have a higher chance of developing constipation and related complications such as stool impaction and bowel perforation.

Development of hypertension and worsening of pre-existing hypertension have been reported following the use of Aimovig® in the postmarketing setting. Many of the patients had pre-existing hypertension or risk factors for hypertension. There were cases requiring pharmacological treatment and, in some cases, hospitalization. Hypertension may occur at any time during treatment but was most frequently reported within seven days of dose administration. In the majority of the cases, the onset or worsening of hypertension was reported after the first dose. Aimovig® was discontinued in many of the reported cases.

We will monitor patients treated with Aimovig® for new-onset hypertension, or worsening of pre-existing hypertension, and consider whether discontinuation of Aimovig® is warranted if evaluation fails to establish an alternative etiology.

The pre-filled syringe may cause pain or discomfort in addition to bleeding, bruising, redness, warmth, itching, swelling, infection, or firmness of the skin near the injection site. Additionally, the pre-filled syringe contains a dry natural rubber that is derived from latex, which may cause an allergic reaction. Subjects who have a known allergy to latex will be excluded.

2.3.2 KNOWN POTENTIAL BENEFITS

Potential benefits of erenumab include an improvement in severity and frequency of facial pain and other sinus-type symptoms in adults, leading to significant improvements in quality of life. This is based on randomized trials demonstrating the efficacy of erenumab.[9, 10, 12] Anecdotally, patients presenting to the otolaryngologist with idiosyncratic facial pain without rhinosinusitis have improvement in facial pain and other sinonasal symptoms with erenumab. Notably, the degree of improvement in facial pain was comparable to that of headache.[2, 13]

2.3.3 ASSESSMENT OF POTENTIAL RISKS AND BENEFITS

Large randomized trials have demonstrated the positive safety profile and efficacy of erenumab versus placebo.

3 STUDY DESIGN

3.1 OVERALL DESIGN

This is a Phase IV, randomized, double-blinded, placebo-controlled single center trial of erenumab versus placebo in patients with mid-facial pain or pressure without evidence of sinus disease. Sixty-six eligible subjects will be randomized in a 1:1 ratio to receive subcutaneous injections of either 140 mg erenumab or placebo every 30 days for 6 months (last injection at day 150), followed by a final follow-up visit at day 180.

3.2 EVALUATION BY STUDY VISIT

See Section 1.3, Schedule of Events

3.2.1 SCREENING/LEAD-IN PERIOD (VISIT 1)

Subjects will undergo a screening visit to determine eligibility to proceed with the one month (30-day) lead-in period. The screening visit may be combined with a standard of care visit for patients already being evaluated for rhinosinusitis and/or facial pain. This study will be explained in lay language to each potential participant. Each participant will sign an informed consent before committing to any study-related tests or procedures. The screening visit will occur at least 30 days before Visit 2 and will include the following assessments:

1. Written informed consent
2. Assessment of prior & current concomitant medications
3. Record demographics
4. Complete medical history physical exam. Only perform if not previously done as SOC in the 30-day screening period.
5. Vital signs, height and weight
6. Endoscopy. If performed as SOC within 3 months prior to enrollment, it may be used. If a SOC endoscopy was performed more than 3 months before enrollment or was never performed, it will be performed for study purposes.
7. Complete sinus CT scan and nasal endoscopy if not completed as standard of care within 12 months of randomization
8. Pregnancy test (serum), if applicable
9. Completion of questionnaires
 - a. Migraine Assessment Tool (MAT)
 - b. 22-Item Sinonasal Outcomes Test (SNOT-22)
 - c. Migraine Functional Impact Questionnaire (MFIQ)
 - d. Pain Location Diagram

10. Review pain diary with subject [ecological momentary assessment (EMA)] - how and when to complete.
11. Discuss compensation with subject.
12. Collect baseline adverse event information, if applicable.

During the screening visit, eligible subjects will receive instructions and training on use of the ecological momentary assessment (EMA) via mobile phone. If for any reason they cannot complete the EMA via a mobile phone, a paper copy will be available to the participant. During the 30-day lead-in period, subjects will be expected to score on a scale of 1 to 10 their symptoms of pain/pressure, nasal congestion, and rhinorrhea as well as any rescue medicines taken for pain each day. Subjects will be instructed to return to the site at the end of the 30-day lead-in period for Visit 2. During the 30-day lead-in period, subjects must record a minimum of 20 (67%) daily diary entries to be eligible for randomization during visit 2. This will be evaluated through the review of the EMA daily data log. The coordinator may call subjects to remind them to complete the log during this time period. Subjects who do not have a minimum of 20 daily entries will be considered a screen failure and removed from the study.

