3.2.2 BASELINE/RANDOMIZATION (VISIT 2)

At the end of the 30-day lead-in period, subjects will return to the study site for visit 2. Eligibility criteria will be reviewed, including review of the EMA data during the lead-in period. If study participant meets eligibility based on review of baseline assessments, then subjects will be randomized and receive the first dose of erenumab or placebo.

Assessments to be performed during visit 2:

1. Concomitant medication review
2. Physical exam
3. Vital signs, height and weight
4. Pregnancy test (urine) if applicable
5. Review of data from EMA with instructions for continued use
6. Randomization
7. Administration of placebo or IP

Subjects will be given a portable home blood pressure monitoring device. Instructions for use of this device will be provided at the time of the first dose of the study drug. Subjects will record their blood pressure every day for seven consecutive days after the first dose. Thereafter, they will record their blood pressure once per week and when symptomatic throughout the entire duration of the study. Subjects will enter their blood pressure information through redcap or twilio. This data will be reviewed monthly by the PI or within 24 hours if immediate intervention is required. In addition, patients will be educated on the symptoms of high blood pressure and, at any time in the study, if symptomatic, the patient should check their blood pressure and notify the study coordinator. The coordinator may call the subject to remind them to record their blood pressure during their study participation.

For patients with normal baseline blood pressure (at or below 120/80), if subjects find that their blood pressure equals or exceeds 140 mm Hg systolic or 90 mm Hg diastolic on two consecutive readings within thirty minutes, they will notify the study coordinator and seek medical attention. For patients who have abnormal baseline blood pressure, if subjects find that their blood pressure equals or exceeds 160 mm Hg systolic or 100 mm Hg diastolic on two consecutive readings within 30 minutes, they will notify the study coordinator and seek medical attention. Subjects will be asked to repeat the pressure the following day. If persistently elevated for three consecutive days, subject will be removed from the study and referred for evaluation and treatment.

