4.2 EXCLUSION CRITERIA

1. Hypersensitivity to erenumab or to any of the drug components (acetate, polysorbate, and sucrose).
2. Previous exposure to erenumab or any other -CGRP inhibitor in the six months prior to enrollment.
3. Allergy to latex.
4. Inability to differentiate facial pain from other headaches.
5. Non-English speaking or unable to provide written informed consent.
6. On a preventative migraine medication (see below) during the 30 day lead-in period:
 - Category 1: Divalproex sodium, sodium valproate
 - Category 2: Topiramate
 - Category 3: Beta blockers (for example: atenolol, bisoprolol, metoprolol, nadolol, ebivolol, pindolol, propranolol, timolol)

- Category 4: Tricyclic antidepressants (for example: amitriptyline, nortriptyline, protriptyline)
- Category 5: Serotonin-norepinephrine reuptake inhibitors (for example: venlafaxine, desvenlafaxine, duloxetine, milnacipran)
- Category 6: Flunarizine, verapamil
- Category 7: Lisinopril, candesartan

7. Received botulinum toxin (Botox) to the head and neck for migraines in the last four months.
8. More than one major open surgery of the nose or sinuses for sinonasal cancer.
9. History of uncontrolled or unstable blood pressure.
10. History of liver failure.
11. History of metastatic malignancy in the last five years or actively undergoing treatment for cancer.
12. Active seizure disorder or other significant neurological conditions other than migraine.
13. Myocardial infarction (MI), stroke, transient ischemic attack (TIA), unstable angina, or coronary artery bypass surgery or other revascularization procedure within 12 months prior to screening.
14. History or evidence of any other unstable or clinically significant medical condition that in the opinion of the sponsor-investigator/ Principal Investigator, would pose a risk to subject safety or interfere with the study evaluation, procedures or completion.
15. Evidence of drug or alcohol abuse or dependence within 12 months prior to screening, based on medical records or patient self-report.
16. Pregnant or breastfeeding, or expecting to conceive during the study, including through 16 weeks after the last dose of investigational product or placebo

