8.4.3 ANALYSIS OF THE SECONDARY ENDPOINT(S)

- The mean number of days per month with significant pain or pressure

This will be compared between baseline and 1, 3, and 4-6 months within each group. This represents an intragroup analysis as opposed to comparing treatment and placebo groups.

- 22-Item Sinonasal Outcomes Test (SNOT-22)

The change in mean scores from baseline for the SNOT-22 survey will be compared at 1, 3, and 6 months. The SNOT-22 is the most widely-used validated sinonasal questionnaire in the otolaryngologic literature.[16] Respondents rate the severity of twenty-two symptoms from a scale of 0 (no problem) to 5 (severe as can be) over the previous two weeks, for a score ranging from 0 to 110. It is self-administered and includes symptoms pertaining to multiple domains, including nasal, extranasal, sleep, and psychological. A minimal clinically important difference has been determined to be 9.[17] Analysis of the SNOT-22 will allow the assessment of changes in specific sinonasal symptoms, such as drainage and congestion, which are thought to be associated with idiosyncratic facial pain.

- Migraine Functional Impact Questionnaire (MFIQ)

The change in mean scores from baseline for each of the five subdomains of the MFIQ will be compared at 1, 3, and 6 months. The MFIQ is a self-administered 26-item questionnaire assessing the impact of migraine on five domains over the previous seven days: physical functioning (5 items), usual activities (10 items), social functioning (5 items), emotional functioning (5 items), and overall functioning (1 item).[18,19] Each item is rated on a 5-point scale, with 5 representing the greatest impact. The scores for each domain will be calculated as the sum of the items.

- Change in number of doses of rescue medication use for facial pain

The change in number of doses of rescue medication use from baseline to 1, 3, and 4-6 months will be compared. The daily data log will enable analysis of frequency, type, and numeric dose of the following rescue medications: triptans, opiates, tramadol, acetaminophen-containing medications, butalbital, antihistamines, non-steroidal anti-inflammatory drugs, decongestants, antibiotics, and steroids. The frequency (number of doses) of rescue medication use will be compared between the two groups at baseline and 1, 3, and 4-6 months

- Mean daily pain score

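### SNOT-22 and MFIQ are not measured at Visit 2, so their only pre-dose scores are at least a month old and predate the lead-in that supplies the diary baselines

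*Combined protocol and SAP*

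**What the plan says.** **When the forms are given.** Section 3.2.1 puts SNOT-22 and MFIQ among the Visit 1 questionnaires (items 9b and 9c) and fixes the timing: "The screening visit will occur at least 30 days before Visit 2 and will include the following assessments". Section 3.2.2, under "Assessments to be performed during visit 2", lists seven items and no questionnaire, although this visit is titled as the baseline visit and the first dose is given there. The schedule of events (1.3) agrees with both lists: each form is marked at Visits 1, 5 (Day 90) and 8 (Day 180), and Visit 2 is blank.

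**How they are used.** Sections 1.4 and 8.1 define both as change from baseline at 1, 3 and 6 months, and 8.1 frames the comparison as treatment against placebo. Section 8.4.2 puts the baseline value in the mixed model as a covariate and reports least squares means for each arm as well as the difference. Section 8.4.3 applies the same methods to the secondary endpoints. No section defines baseline for the questionnaires.

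**Recall periods (8.4.3).** SNOT-22 asks about symptoms "over the previous two weeks, for a score ranging from 0 to 110". MFIQ is described as "assessing the impact of migraine on five domains over the previous seven days".

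**Context of Visit 1.** "The screening visit may be combined with a standard of care visit for patients already being evaluated for rhinosinusitis and/or facial pain" (3.2.1). Exclusion 6 in 4.2 applies to a subject "On a preventative migraine medication (see below) during the 30 day lead-in period". No washout before Visit 1 is stated.

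**The concern.** The visit called baseline collects no baseline for these two instruments, so the Visit 1 score has to serve by default. Two things follow.

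First, the trial reports change from baseline against two different pre-treatment periods without saying so. Pain days, congestion and rhinorrhea days, rescue doses and mean pain score are referred to the lead-in month. SNOT-22 and MFIQ are referred to the one or two weeks before it. The arm-level mean changes on the questionnaires therefore contain a month with no study drug. That month could include settling after the screening visit. It could also include a change of medication, if any subject stopped a preventive just before the lead-in.

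Second, the covariate is further in time from the outcome than it need be. An older baseline usually correlates less with the outcome and removes less variance, and the trial randomises only 66 subjects.

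**Working it through.** **1. The plan's own figure.** The sample size (8.2) concerns pain days only: difference 3.0, SD 3.5, two-sided 0.05, 90% power. The normal approximation gives n = 2 × (3.5/3.0)² × (1.960 + 1.282)² ≈ 28.6, so 29 per group, and 29/0.9 = 32.2, so 33. The stated 33 is reproduced. It does not depend on the questionnaires, and the plan states no power, SD or correlation for them.

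**2. Timing.** Take Visit 1 on Day -30 and Visit 2 on Day 0 to +6 (1.3).
- Gap from questionnaire baseline to first dose: 30 to 36 days.
- SNOT-22 recall: -30 - 14 = -44, so about Days -44 to -30.
- MFIQ recall: -30 - 7 = -37, so about Days -37 to -30.
- Diary baseline: the 30 days that follow Visit 1.

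The questionnaire and diary baseline periods do not overlap. With the forms at Visit 2, the windows would be about Days -14 to 0 and -7 to 0, inside the lead-in.

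**3. Bias between arms.** Visit 1 precedes randomisation and is the same reference in both arms, so no bias is expected. A simulation confirms this on assumed inputs: 30 per arm, true effect -0.5 SD, baseline-outcome correlation 0.5, Visit 1 scores 0.4 SD above Visit 2. The adjusted treatment difference averaged -0.50 with either baseline. The placebo arm's mean change was -0.40 SD from Visit 1 and 0.00 from Visit 2. The second result returns the 0.4 SD shift that was put in. It shows where drift appears, not how large it will be.

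**4. Precision, first-order decay.** With baseline adjustment, residual variance is proportional to 1 - ρ². Let the correlation at lag k months be r^k. The lag to Day 90 is 4 months from Visit 1 and 3 from Visit 2; to Day 180 it is 7 and 6. The variance ratio (Visit 1 over Visit 2) is (1 - r^(2b))/(1 - r^(2a)), with a the shorter lag and b the longer. The standard error ratio is its square root.

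| r (assumed) | Day 90 variance ratio | SE ratio | Day 180 variance ratio | SE ratio |
|---|---|---|---|---|
| 0.80 | 0.832/0.738 = 1.13 | 1.06 | 0.956/0.931 = 1.03 | 1.01 |
| 0.85 | 0.728/0.623 = 1.17 | 1.08 | 0.897/0.858 = 1.05 | 1.02 |
| 0.90 | 0.570/0.469 = 1.22 | 1.10 | 0.771/0.718 = 1.07 | 1.04 |

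**5. Precision, mostly stable correlation.** Keep the one-month correlation at 0.85, but let 0.7 be a stable patient component: ρ(k) = 0.7 + 0.3 × 0.5^k, which gives ρ(1) = 0.85.
- Day 90: ρ(3) = 0.7375 and ρ(4) = 0.71875. Ratio (1 - 0.5166)/(1 - 0.5439) = 0.4834/0.4561 = 1.06; SE ratio 1.03.
- Day 180: ρ(6) = 0.7047 and ρ(7) = 0.7023. Ratio 0.5067/0.5034 = 1.007; SE ratio 1.003.

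No one-month figure is given, because neither form is scheduled at Day 30. That is a separate matter.

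**The case against.** The best defence is that a screening score taken before randomisation is a valid covariate, and that nothing the plan tests on these forms is biased by its age. This stands. SNOT-22 and MFIQ are compared between arms only. The sole planned within-arm comparison is on pain days, so drift during the untreated month reaches only the reported least squares means by arm.

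The precision loss rests on an assumed correlation. Section 8.4.2 names a first-order autoregressive structure, if applicable, which gives the decay model some support. That model has no stable patient component, however, and with one the loss at Day 180 nearly disappears. This also stands, and is why both cases are shown.

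Visit 2 scores would not make arm-level changes clean either. Section 4.3 requires at least 10 significant-pain days in the lead-in. A Visit 2 score whose recall falls in that month is exposed to the same selection, and so to some regression to the mean. No questionnaire score is itself an entry criterion. Arm-level changes would still not be treatment effects, but they would share a reference period with the diary outcomes.

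The defence does not explain why the baseline visit omits the two forms, and no reason is given.

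**Conclusion.** The omission is clear: the Visit 1 list, the Visit 2 list and the schedule all agree. Both instruments have a single pre-dose score, at least 30 days old at first dose and referring to a period before the lead-in. The effect is modest and confined to secondary endpoints. Standard errors are about 6% to 10% larger at Day 90 and 1% to 4% larger at Day 180 under first-order decay with monthly correlation 0.80 to 0.90, or about 3% and 0.3% larger if most of the correlation is stable. Arm-level mean changes also include an untreated month, whose contribution cannot be sized from the documents.

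A reader might infer more than this, and the documents do not support it:
- **That the treatment comparison is biased.** The reference precedes randomisation and is the same in both arms.
- **That the questionnaire baselines are taken on preventives.** Exclusion 6 leaves this possible for someone who stopped before the lead-in. Nothing says subjects will do so, and the frequency is unknown.
- **That Visit 1 is a care-seeking visit for everyone.** Section 3.2.1 only permits combining it with standard care. Inclusion criterion 1 points that way, but 4.4 also recruits by outside referral and social media.
- **That arm-level changes will be judged against the SNOT-22 minimal important difference of 9.** Section 8.4.3 gives that figure as background; no responder rule or threshold uses it.

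One reading needs care. The schedule heads the Visit 1 column Day -30 to -1. Read as the lead-in span, this agrees with 3.2.1. Read as a visit window, it conflicts and should be reconciled.

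**What to change.** 1. In 1.3, mark SNOT-22 and MFIQ at Visit 2.
2. In 3.2.2, list both forms, to be completed before randomisation and the first injection.
3. In 1.4 and 8.4.3, define the Visit 2 score as the baseline for both instruments, and keep the Visit 1 score as descriptive.
4. If any subjects have already passed Visit 2, state in 8.4.3 how they are handled, because a Visit 2 score cannot be recovered later.

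The cost is protocol wording and slight patient burden: two self-completed forms of 22 and 26 items at a visit every randomised subject already attends. The sample size and the primary analysis do not change.
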